4.4 Sample size calculation

We carefully determined the required number of patients to ensure reliable outcome estimates in collaboration with co-creating stakeholders and by consulting orthopaedic surgeons using an online survey on what constitutes convincing evidence. The agreed sample size is 250 patients per group. Therefore, we plan to randomize 250 patients per study group resulting in a total of 750 THA and 750 TKA patients.

To provide a rough indication of the statistical power, we used the online power calculator tool available on Sealed Envelope [20]. The sample size calculation is based on the comparison of RFU vs. active COD as the primary analysis. For this calculation, we assumed that the actual complication rate in both groups is 10%. With the agreed number, it is possible to detect a clinical relevant difference of 10% in complications between the two groups. If there is truly no difference between active COD and RFU, 190 patients per group are needed to be 80% sure that the limits of a two-sided 95% confidence interval will exclude a difference between active COD and RFU of more than 10%. Anticipating 20-25% loss to follow up, we plan to randomize 250 patients.

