10. STATISTICAL ANALYSIS

All analyses will be performed separately for THA and TKA and will be performed using IBM SPSS statistics (SPSS software version 28.0) or R. Categorical data will be presented as numbers and percentages. Continuous variables will be presented by mean and standard deviation in case of a normal distribution. In case of non-normality, median and interquartile range will be given.

Mixed models are used to deal with missing data; when necessary and possible we will perform multiple imputation.

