For the budget impact analysis we plan to use the BIA tool as suggested and provided by ZonMw. The BIA will be based on the Dutch population, and hence Dutch incidence data will be used. Perspectives that will be considered are the societal, government (Budget Kader Zorg), and insurer perspective. Different scenarios will be evaluated including the following: 1) the intervention is not implemented, i.e. all patients will receive RFU only, 2) the intervention is offered to the whole patient population, i.e. all patients receive COD, and 3) the intervention is only offered to specific subgroups of the potential patient population, such as patients with the lowest risk of complications. These subgroups will be defined based on the results of the study, e.g. subgroups who particularly benefit from the intervention. The cost of the intervention mix will be valued using Dutch standard costs for the societal perspective, actual NZA tariffs for the government perspective, and average tariffs NZA for the insurer perspective.

This cost-effectiveness and budget impact analysis will comply with the 'Dutch guideline for economic evaluations in health care' [31].

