10.4 Exploratory analysis

As an exploratory analysis, we will assess subgroup effects on the primary outcomes of complications, clinical visits and X-rays. The GLMMs described above will be extended by including interaction terms for age, gender, BMI, ASA, ethnicity, employment status and educational level with the intervention in separate models.

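### Budget impact scenario 3 may choose its COD subgroups on the benefit observed in the trial itself; fix them beforehand by baseline complication risk (minor)

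*Protocol*

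**What the plan says.** Protocol section 10.2.1 sets out three scenarios for the national budget impact analysis. In the first, everyone keeps routine follow-up (RFU). In the second, "the intervention is offered to the whole patient population, i.e. all patients receive COD". In the third, "the intervention is only offered to specific subgroups of the potential patient population, such as patients with the lowest risk of complications". The next sentence states how the third scenario's patients are found: "These subgroups will be defined based on the results of the study, e.g. subgroups who particularly benefit from the intervention".

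Section 10.4 is the only place that describes treatment effects by subgroup. It is labelled exploratory: "we will assess subgroup effects on the primary outcomes of complications, clinical visits and X-rays". The models are extended by "including interaction terms for age, gender, BMI, ASA, ethnicity, employment status and educational level with the intervention in separate models". Section 10 adds: "All analyses will be performed separately for THA and TKA".

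No significance level or multiplicity correction is given for these interactions, and no threshold is given for choosing a subgroup. Section 10.2.1 does not refer to section 10.4. It also does not say whether subgroup-specific trial estimates will enter the budget calculation.

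**The concern.** Section 10.2.1 offers two bases for the scenario 3 subgroup, and they differ in kind. Low complication risk is prognostic and can be established without looking at the treatment comparison. Particular benefit is a treatment-effect criterion, and the sentence has it read off the trial results. The choice between the two stays open until those results are known.

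If benefit is the criterion, the search runs over many small, uncorrected contrasts. A subgroup that stands out may do so by chance. If its effect is then taken from the same data, that effect is inflated by the selection.

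At stake is a projection for the Dutch population from societal, government and insurer perspectives. It could name patient groups by age, ethnicity or education as the ones suited to COD. Section 3 records that the orthopaedic association commits to implementing the results, so a named subgroup could be acted on.

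**Working it through.** **The plan's own figure.** The protocol gives no error rate for the subgroup step. The figure that can be reproduced is the sample size in section 4.4, which also supplies the inputs below: a 10% complication rate in both groups, a 10-point margin, 80% power and a two-sided 95% interval. With the type II error split over two limits, n = 2 × 0.10 × 0.90 × (1.960 + 1.282)² / 0.10² = 189.1, so 190 per group as stated. Allowing 24% loss, 190 / 0.76 = 250, which agrees with 250 randomised per group and joint.

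**Number of interaction tests.** Section 10.4 lists 7 covariates and 3 outcomes, and section 10 separates 2 joints: 7 × 3 × 2 = 42, counting one test per covariate.

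**Chance of at least one false interaction.** Assumptions not in the protocol: each test at two-sided 0.05, and no true interaction. The only error level in the document belongs to the sample size, where the aim is that "the limits of a two-sided 95% confidence interval will exclude a difference between active COD and RFU of more than 10" per cent. For k independent tests the chance is 1 − 0.95^k.

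| Tests counted | k | Chance of at least one |
|---|---|---|
| Complications, one joint | 7 | 30% |
| Complications, both joints | 14 | 51% |
| All three outcomes, one joint | 21 | 66% |
| All three outcomes, both joints | 42 | 88% |

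Tests on correlated outcomes and covariates give less. For all 42, simulation with assumed correlations gives:
- 85% with outcome correlations of 0.3 and, for visits with X-rays, 0.7;
- 80% with 0.5 and 0.9;
- 73% with 0.8 and 0.95;
- 71% with 0.7 and 0.95 plus a correlation of 0.3 between covariates.

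Counting a significant result in only one pre-named direction (0.025 per test) gives 65% for 42 independent tests and about 42-60% for correlated ones.

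**Size of the selection effect, without any test.** Assume seven roughly even binary splits, hence 14 subgroups per joint. Take a 10% complication rate in both arms and a true difference of zero, and always choose the subgroup that looks best for COD. In a half-sized subgroup the standard error of the difference in proportions is √(2 × 0.10 × 0.90 / 95) = 4.4 points at 190 per arm, and √(2 × 0.10 × 0.90 / 125) = 3.8 points at 250. Across simulations with different covariate correlations and either binary or Poisson complications, the chosen subgroup shows on average 5.1 to 5.6 points fewer complications under COD at 190 per arm, and 4.3 to 4.9 at 250. About 93-94% of simulated trials contain at least one subgroup that favours COD.

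**The case against.** The strongest reply is that the protocol fixes no such selection rule. It does not connect section 10.4 to the budget analysis, set a threshold, or say that one significant interaction is enough. Benefit is only an example, and low complication risk is named before it. Results of the study could also mean a risk estimate from the adjusted complication models in section 10.1, to which no false-interaction rate applies. All of this stands. It is why the percentages are illustrations and why the narrow readings belong beside the wide one.

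A reader might infer that the plan will find a benefiting subgroup 70-88% of the time when none exists, and that scenario 3 is therefore biased towards COD. The documents do not support that. The percentage requires all 42 tests to act as the selector at 0.05. The bias requires both selection on observed benefit and reuse of the same data for the effect, and the second step is not stated. A budget analysis also counts the scheduled visit and X-ray that COD removes by design, and that saving is not produced by selection. No bias in euros can be computed from the document.

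An assumption of no interaction is also doubtful for visits and X-rays: RFU schedules them for everyone, while on-demand use may truly differ between patients. The complications-only figures and the best-of-14 result do not depend on those outcomes.

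Finally, thresholds and multiplicity handling can be left to a statistical analysis plan, and section 10.4 is already labelled exploratory. That is fair for section 10.4. It does not answer the sentence in section 10.2.1, which positively allows selection on the results. An analysis plan that fixed the subgroup beforehand would have to depart from it.

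**Conclusion.** The point holds in a conditional form. Section 10.2.1 allows the scenario 3 subgroup to be chosen on the observed effect after the results are known, and the only effect-by-subgroup analyses described are exploratory and have no stated correction. If that route is taken, the chosen subgroup may be chance. If its effect comes from the same data, scenario 3 will be over-optimistic for COD in that group.

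At an assumed two-sided 0.05 with no true interaction, the chance of a false lead is 30%, 51%, 66% or 71-88%, depending on which tests are counted and how they correlate. Simply taking the best of 14 assumed binary subgroups gives an apparent advantage of about 4 to 5.5 percentage points against a 10% rate.

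One scenario of a secondary economic projection is affected. Scenarios 1 and 2, the primary analysis and the incremental cost-effectiveness ratios are not. Severity is minor, and the change is a cheap improvement.

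**What to change.** In section 10.2.1, replace the sentence that defines the subgroups from the study results. Suggested content:

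- The scenario 3 subgroup is defined by baseline risk of complications, a basis the section already names. Risk comes either from a prognostic model fitted on the pooled arms without a treatment term, or from the history between surgery and 10 years listed in section 8.1.3. The definition and cut-off are fixed before the arm comparison is seen.
- The overall COD-RFU effect for each joint is applied on the relative scale to that subgroup's own baseline risk. The scale must be stated, because carrying an absolute difference over to a deliberately low-risk group would misstate its complications.
- Any additional scenario based on an observed interaction is labelled exploratory and uses a shrunken estimate.

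A strict multiplicity gate is not advised as the main device. Over 42 tests the first Holm step is 0.05 / 42 = 0.0012, or z = 3.24. With a 10% rate and an even split, each of the four cells holds 9.5 expected events at 190 per arm, so the standard error of the log ratio of rate ratios is √(4 / 9.5) = 0.649 and the ratio needed is exp(3.24 × 0.649), about 8. At 250 per arm the cells hold 12.5 events and the ratio needed is exp(3.24 × 0.566), about 6. That is close to a ban.

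The cost is one paragraph and a simple risk model. The model must stay small: RFU and active COD together would supply about 2 × 190 × 0.10 = 38 to 2 × 250 × 0.10 = 50 complications per joint. The downside is that a genuine but modest interaction will not drive scenario 3.

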10.3 Other study parameters

Other study parameters, like patient characteristics and surgical information, will be given as numbers and percentages in case of categorical data. Continuous variables will be presented by mean and standard deviation in case of a normal distribution. In case of non-normality, median and interquartile range will be given. These parameters will be used to describe the included population and the clinical visits, but also to adjust the intervention effects.

10.4 Exploratory analysis

As an exploratory analysis, we will assess subgroup effects on the primary outcomes of complications, clinical visits and X-rays. The GLMMs described above will be extended by including interaction terms for age, gender, BMI, ASA, ethnicity, employment status and educational level with the intervention in separate models.

10.5 Interim analysis (if applicable)
NA

11. ETHICAL CONSIDERATIONS

11.1 Regulation statement

The study will be conducted according to the principles of the Declaration of Helsinki (version 8, October 2024) and in accordance with the Medical Research Involving Human Subjects Act (WMO) and other guidelines, regulations and Acts.

11.2 Recruitment and consent

First, each participating center will select patients who had a THA or TKA 10 years ago using the LROI register and EPD. From this list, all patients will be selected who meet the inclusion and exclusion criteria. From the remaining list, patients will be randomized in a 1:2 ratio into a passive and active group. Patients in the active group will be approached for participation.

The initial contact regarding the study will be made by a physician working in the orthopaedic department of the hospital where the surgery was performed, by asking permission if he/she can be approached for the study. A researcher or research coordinator will contact the patient by phone, or at the outpatient department to assess their suitability for participation based on their medical history and the study's inclusion and exclusion criteria. The researcher will provide a brief overview of the study's purpose and procedures and offer the opportunity for patients to ask any initial questions about the study. If the patient expresses interest in the study, the patient information letter including the informed consent form will be sent by mail, along with a return envelope, and/or e-mail ensuring the patient has adequate time to review the study details. The patient will be contacted after at least 5 days by the research team. The researcher will discuss the patient information letter and the patient has the opportunity to ask further questions. Once the patient agrees to participate, they will sign the consent form and return it to the research team. The researcher will sign and return a copy of the fully signed consent form to the patient, ensuring that both the investigator and the patient have a complete signed informed consent.

There is also an option for e-consent using Castor EDC, which safely collects and stores data in compliance with Good Clinical Practice (GCP). The e-consent and screening procedures will maintain an audit trail to record data entries with timestamps and editors. Access to the Castor EDC study page will be limited to the research team. Research has shown that e-consent improves participants' understanding of clinical trial information and is rated as a more acceptable and user-friendly consenting process compared to traditional paper-based methods. The first part of recruitment is identical to the hard-copy procedure, but if the patient expresses interest in learning more about the study, the researcher will send an email to the patient containing a personalized URL. By clicking this URL, patients will

access an introductory screen in Castor EDC, where the patient information letter is provided. Here, it is explained how a participant can revoke their consent during the study. The patient will still be contacted after at least 5 days by the research team, the researcher will discuss the patient information letter and the patient has the opportunity to ask further questions. If the patient is interested in participation, they can confirm this with an electronic informed consent (e-consent) using a Castor EDC survey presented after the digital patient information letter. In this survey, the patient can confirm their understanding of the information and willingness to participate in the study. Using locked checkboxes (yes/no), the patient can give permission to additional questions (similar as in the hard-copy procedure). Additionally, the patient need to select the date they signed the consent. The consent procedure will be completed only if all boxes are selected. The participant will receive a copy of this informed consent form, signed by a researcher, by email.

11.3 Benefits and risks assessment, group relatedness

We expect that participants will not have benefits from participating to the study. There are no additional risks expected compared to standard care, as both RFU and COD at 10 years after THA or TKA are part of current clinical care. Patients are asked to spend time to fill out questionnaires. Only the RFU group will be asked to spend time to visit the hospital.

11.4 Compensation for injury

The sponsor/investigator has a liability insurance which is in accordance with article 7 of the WMO. The METC gives dispensation for research participant insurance, because no additional risks are expected as RFU and COD are both part of standard care.

11.5 Incentives (if applicable)

Participants will not receive any incentives or compensation as both COD and RFU are standard care.

12. ADMINISTRATIVE ASPECTS, MONITORING AND PUBLICATION

12.1 Handling and storage of data and documents

Data are handled confidentially and anonymously. All participants participating in this study will be linked to a participant identification code based on the center from which they participate (e.g. RHOC001 till RHOC150). The key to the code is safeguarded by the local investigator of the participating center. During the study, the investigator also has access to the key and contact details of the participants to be able to send reminders and contact patients to fill in the questionnaires. All contact details will be deleted at the investigator site after study completion.

Data will be stored for 15 years by each participating center. All data will be processed and analysed with the participant identification code by the investigator. Also, in reports and publications only the participant identification code will be used. The research team, and where appropriate, monitors and staff of the IGJ have access to source documents. These persons will keep all data secret.

All data will be collected in the web-based database Castor EDC. Questionnaires will be sent from the Castor EDC and filled in by the patient. For these data direct entry is applicable. Other data will be collected from the EPD and LROI register. Participants will also give permission to use the data for other studies or not.

Patients can leave the study of his own volition. In case data are already collected, these data will be used in the study unless the patient also revoke the consent to use the collected data.

The handling of personal data will comply with the EU General Data Protection Regulation and the Dutch Act on Implementation of the General Data Protection Regulation. (in Dutch: Uitvoeringswet AVG, UAVG).

12.2 Monitoring and Quality Assurance

Monitoring will be performed in compliance with Good Clinical Practice (GCP) and other rules and regulations in order to achieve high quality research and secure patient safety. Qualified and independent monitors will have access to the data and source documents. The study will be monitored annually by an independent member of the research department of the Reinier Haga Orthopedisch Centrum, who is not involved in this study.

12.3 Amendments

Amendments are changes made to the research after a favourable opinion by the review committee has been given. All amendments will be notified to the review committee that gave a favourable opinion.

Non-substantial amendments will not be notified to the review committee, but will be recorded and filed by the sponsor.

12.4 Annual progress report

The sponsor/investigator will submit a summary of the progress of the trial to the review committee once a year. Information will be provided on the date of inclusion of the first participant, numbers of participants included and numbers of participants that have completed the trial, serious adverse events, other problems, and amendments.

12.5 Temporary halt and (prematurely) end of study report

The investigator/sponsor will notify the review committee of the end of the study within a period of 8 weeks. The end of the study is defined as the end of follow-up of the last patient. The sponsor will notify the review committee immediately of a temporary halt of the study, including the reason of such an action.

In case the study is ended prematurely, the sponsor will notify the review committee within 15 days, including the reasons for the premature termination.

Within one year after the end of the study, the investigator/sponsor will submit a final study report with the results of the study, including any publications/abstracts of the study, to the review committee.

12.6 Public disclosure and publication policy

In accordance with the requirements of the International Committee of Medical Journal Editors, the study will be registered in a public trial registry prior to the recruitment of the first patient. The results will be published in peer-reviewed scientific journals and presented at relevant (inter)national congresses. The arrangements for public disclosure and publication of the research data for the overall HAKA project are outlined in the ZonMw consortium agreement between the sponsors of the individual studies. For the participating centers within the studies, publication policies are specified in the Participation Agreements.

13. STRUCTURED RISK ANALYSIS

NA

